#### 4.3.3 Intervention Periods

Each of three feeding periods lasts 6 weeks, during which time participants are provided all of their food, snacks and most beverages. A washout period of at least 2 weeks separates each period; the washout period allows ad libitum food intake. Participants are fed sufficient calories to maintain their weight. During the initial four weeks of each period, BP is measured once each week. During the last 10 days of each intervention period, BP is measured on 5 days; 2 days of these 5 measurement days occur during the last 5 days of the intervention period. The requirement for 5 measurements during the last 10 days (2 measurements during the last 5 days) of each period ensures that participants will have been exposed to the diet for the full 6 weeks of feeding.

During the last 10 days, one 24 hour collection of urine is also obtained. A fasting blood specimen is drawn during the 4th and 6th week of each intervention period. For each day of controlled feeding, participants complete a daily diary. In the first and last week of each intervention period, participants also complete a symptoms questionnaire. During the last week of the last feeding period, participants complete an anonymous adherence questionnaire.

Table 3 displays major measurements and data collection activities by visit. The following sections describe our approach to measuring all outcomes variables and other selected measurements.

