# 4.11 Analysis plan

Primary analyses compare the BP and plasma lipid concentrations measured at the end of the CARB diet with those at the end of the PROTEIN and UNSAT diets, within each individual among all participants.

*Outcome definitions*. For **Specific Aim 1**, the primary outcome is constructed as follows. The SBP measure associated with a given diet is the mean of the five SBP measures obtained in the final two weeks of the intervention period for that diet. The primary outcome for each participant for the PROTEIN diet is the difference between the participant's SBP measure for that diet and the corresponding SBP measure for the CARB diet. The primary outcome for each participant for the UNSAT diet is the difference between the participant's SBP measure for that diet and the corresponding SBP measure for the CARB diet. The secondary outcome for Specific Aim 1 is constructed analogously using DBP instead of SBP measures. For **Specific Aim 2**, the lipid values associated with a given diet are obtained from the week 6 fasting blood sample for that diet. The primary lipid outcome for each participant for the PROTEIN diet is the difference between the participant's LDL-C from that diet and his/her corresponding LDL-C measure from the CARB diet. The primary outcome for each participant for the UNSAT diet is the difference between the participant's LDL-C from that diet and his/her corresponding LDL-C measure from the CARB diet. The primary outcome for each participant for the UNSAT diet is the difference between the participant's LDL-C for that diet and his/her corresponding LDL-C measure from the CARB diet. The primary outcome for each participant for the UNSAT diet is the difference between the participant's LDL-C for that diet and his/her corresponding LDL-C measure from the CARB diet. The primary outcome for each participant for the CARB diet. Other lipid outcomes in **Specific Aim 2** and all outcomes for **Specific Aims 3 and 4** are derived in like fashion for each of the components identified in the statement of the relevant Specific Aim.

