*Analysis framework.* The inferences of interest concern efficacy of the proposed diets in reducing risk of cardiovascular disease. All pairwise comparisons between diets will be evaluated for all outcomes. Primary analyses will be conducted on a per protocol basis, excluding information on study dropouts whenever incompleteness interferes with a given comparison, i.e., an individual who completes only two diets contributes information to only one comparison. Primary analyses will be supplemented by detailed information on dropouts, and by analysis of sensitivity of inferences to the occurrence of dropouts. These secondary analyses will investigate patterns of missingness, will attempt to discern if missingness is associated with features of the response profile, and will employ multiple imputation from the posterior predictive distribution of the outcome on the opposing arm to obtain a conservative secondary inference. The standard multiple imputation variance (Rubin, 1987) will be used to obtain secondary test statistics and confidence intervals. In the previous DASH trials, such incompleteness was very rare.

Inferential contrasts will be calculated using the simplest appropriate statistical method. For example, with the SBP outcome, the equal-variances paired t-test of equal blood-pressure effects on two diets will likely be satisfactory. Ninety-five (95) percent confidence intervals will be reported for the effects of PROTEIN and UNSAT relative to CARB. The effect of PROTEIN compared to UNSAT will be reported, but this pairwise contrast is not independent of the other 2 primary comparisons. Supplementary detailed modeling of the trajectory of repeatedly observed outcomes and its dependence on covariates will be conducted in the mixed effects models framework (Laird and Ware, 1982).

*Multiple comparisons*. Statistical significance will be reported without adjustment for multiple comparisons, and all point estimates and p-values will be accompanied by unadjusted 95% confidence intervals for the mean difference. For each analysis, statistical significance will be defined by p (unadjusted) <0.05.

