*Kinetic modeling*. Kinetic modeling of outcomes are used to assess whether a steady state has been achieved. To this end, we also employ mixed effects models. The 6 week duration of the feeding perio makes it feasible to fit detailed models of outcome trajectories. These outcomes include BPs measured weekly during each intervention period and laboratory measurements measured during weeks 4 and 6 of each period. A standard tool is the nonlinear mixed effects model (Pinheiro 2000). For intensively monitored outcomes such as BP components, it is anticipated that asymptotic regressions, that is, of the form mean  $Y = a + (b-a)exp(-c^{*t})$ , where a is final level, b is initial level, and c is a rate constant, can be fit at the individual level. For lipids, glucose and insulin, which are sampled at weeks 4 and 6, inference on variance components corresponding to subject-specific slopes will be used to assess achievement of steady-state kinetics by week 6.

*Carryover effects*. Carryover effects are not expected, given the interval between outcome ascertainment in consecutive periods (at least 8 weeks) and the time course of dietary effects on BP and plasma lipids. Nonetheless, we cannot categorically dismiss the possibility that a small carryover effect could occur. All period

one treatments are free of potential carryover effects; hence, unbiased but inefficient profiles of treatment effects are available using only period one observations. Detection of carryover effects is facilitated by the detailed kinetic modeling described above. If carryover is found for any diet, it will be quantified, and then adjusted estimates of the dietary effects will be provided as secondary analyses. Special designs for the accommodation of carryover effects (Koch 1989; Peace 1990) present drawbacks (e.g., confinement of participants to longer periods with fewer treatments) that are considered undesirable given the low probability of carryover in this setting.

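### The steady-state check for lipids, glucose and insulin looks at the spread of individual slopes between weeks 4 and 6, so it cannot respond to a mean drift that participants share

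*Protocol*

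**What the plan says.** Section 4.11 (Kinetic modeling) states its purpose: "Kinetic modeling of outcomes are used to assess whether a steady state has been achieved". It then treats two groups of outcomes differently.

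- For BP it anticipates an asymptotic curve, "where a is final level, b is initial level, and c is a rate constant", within a nonlinear mixed effects model. The approach of the level to a plateau is therefore modelled directly.
- The second group is introduced with "For lipids, glucose and insulin, which are sampled at weeks 4 and 6". The only criterion named for it is that "inference on variance components corresponding to subject-specific slopes will be used to assess achievement of steady-state kinetics by week 6". The paragraph does not mention the mean week 4 to week 6 change.

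Three other parts of section 4.11 bear on this. The analysis framework promises supplementary mixed-model work on outcome trajectories, without linking it to steady state. The outcome definitions state that "the lipid values associated with a given diet are obtained from the week 6 fasting blood sample for that diet". The carryover paragraph says the kinetic modelling makes carryover easier to detect, but it rests its expectation of no carryover on the interval of at least 8 weeks between outcome readings and on the time course of dietary effects.

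**The concern.** Steady state is a statement about level: on average, values have stopped moving. In a mixed model that is the fixed slope. The variance component of the subject-specific slopes answers another question, namely whether people move at different rates. A variance of zero is compatible with everybody still falling at the same speed, and a large variance is compatible with a mean that is perfectly flat.

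At stake is the steady-state statement for LDL-C, the primary lipid outcome, and for the other lipids, glucose and insulin, together with whatever support the carryover assessment draws from it. This is not a detail left open for a later document. The protocol names a specific criterion, and the criterion addresses the wrong parameter.

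**Working it through.** **Inputs.** n = 160 (section 4.1). Three periods with draws in weeks 4 and 6 (section 4.3.3). SD of LDL-C change 23 mg/dl (section 4.10). Two-sided alpha 0.05, unadjusted (section 4.11). The protocol gives no SD for the week 4 to 6 change, so using 23 for it is an assumption; 15 and 10 were also tried. Drift sizes (0 to -10 mg/dl) and the between-person SD of drift are assumptions too.

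**Step 1: reproduce the plan's figure.** For a paired difference, MDD = (z for alpha + z for power) × SD/√n.
- 80% power: (1.960 + 0.842) × 23/√160 = 2.802 × 1.818 = 5.09.
- 90% power: (1.960 + 1.282) × 1.818 = 5.89.

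Table 5 states 5.1 and 5.9, so the SD is being used as the protocol uses it.

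**Step 2: algebra.** Write the week 6 minus week 4 change of person i in period j as D_ij = μ + s_i + e_ij, where μ is the mean drift, s_i has variance τ² and e_ij has SD 23. The slope variance is tested by comparing the between-person mean square, 3 × Σ(person mean − grand mean)²/159, with the within-person mean square on 320 df. Adding a constant to every D_ij moves each person mean and the grand mean equally, so neither mean square changes. Nor does a drift that differs by diet but is common to people help: everyone takes all three diets, so each completer's mean shifts by the same amount and the between-person mean square is again unchanged.

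**Step 3: mixed-model check.** One simulated data set was refitted by REML after adding common drifts.

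| Added drift (mg/dl) | Fixed slope | Slope variance | Residual variance | Log-likelihood |
|---|---|---|---|---|
| 0 | -0.23 | 8.1046 | 262.69 | -4314.5157 |
| -5.1 | -5.33 | 8.1046 | 262.69 | -4314.5157 |
| -10 | -10.23 | 8.1046 | 262.69 | -4314.5157 |

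Only the fixed slope moves.

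**Step 4: rejection rates** (4,000 simulated trials per row, SD 23).

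| Mean drift | SD of drift between people | Slope-variance test | Mean-change test, one diet |
|---|---|---|---|
| -2.5 | 0 | 0.058 | 0.275 |
| -5.1 | 0 | 0.048 | 0.794 |
| -10 | 0 | 0.052 | 1.000 |
| -5.1 | 2.55 | 0.080 | 0.800 |
| -5.1 | 5.1 | 0.268 | 0.769 |
| -10 | 5 | 0.250 | 1.000 |
| -10 | 10 | 0.949 | 1.000 |
| 0 | 5.1 | 0.258 | 0.049 |
| 0 | 10 | 0.950 | 0.051 |

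At a given spread the slope-variance test behaves alike whether the mean drifts or not: 0.268 against 0.258 at an SD of 5.1, and 0.949 against 0.950 at an SD of 10. With SD(e) of 15 or 10, its rejection rate under a purely common non-zero drift stays between 0.046 and 0.056.

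**Step 5: precision of the direct estimate.** The 95% half-width for one diet's mean change is 1.975 × 23/√160 = 3.6 mg/dl (2.3 at SD 15, 1.6 at SD 10). For the difference in change between two diets, with errors independent across periods, it is 1.975 × 23 × √2/√160 = 5.1 mg/dl.

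**The case against.** The case on the other side is substantial.

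- **No decision rule is stated.** A reader might infer that lipids still falling in everyone would be declared at steady state. The text says only that the variance components will be used in the assessment. A mixed model normally also reports a mean slope, and the supplementary trajectory work would probably show it. This stands: the fault is that the mean slope is not named as the criterion, not that a wrong declaration is certain.
- **The primary analysis does not depend on the check.** A reader might infer that the six-week periods, the week 6 lipid values and the carryover argument all rest on it. They do not. Period length and the week 6 sample are fixed unconditionally, and the carryover expectation has its own grounds. A drift equal on all diets also cancels in the within-person contrasts.
- **Real drift varies between people.** The variance test can then react, as Step 4 shows. But it reacts to the spread, and at SD 23 it has little power until the spread is near 10 mg/dl.
- **A model without a fixed mean slope** would let common drift leak into the variance (rejection 0.26 at -5.1 and 0.95 at -10). The protocol does not say this is intended.
- **Identifiability.** A reader might object that two draws cannot separate a slope variance from residual error. That is so within one diet period, but the protocol speaks of subject-specific slopes, and a slope shared over three periods (six draws) can be estimated.
- **BP.** A reader might extend the point to BP on the ground that no reading at the start of a period is scheduled. In the nonlinear mixed model named, the initial level is an estimated parameter and information is pooled across people, so the document does not support that extension.

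**Conclusion.** The point holds in a limited form. The one steady-state criterion named for lipids, glucose and insulin does not respond to a mean drift common to participants: the result is exact in a mixed model with a fixed mean slope, and the simulated rejection rate stays at alpha at every common drift and SD tried. It also flags stable means when individual slopes differ. Used alone, it cannot justify saying that steady state was reached by week 6, nor strengthen the carryover assessment.

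The primary week 6 contrasts remain valid as comparisons of week 6 values. Their reading as steady-state differences would suffer only if the remaining drift differed between diets. The protocol gives no evidence that such drift exists, and the drift sizes used here are illustrations. The change is worth making because the stated rule is wrong and easily corrected, not because the main results are in danger.

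**What to change.** Replace the criterion in section 4.11 (Kinetic modeling) with wording such as:

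> For lipids, glucose and insulin, steady state will be assessed by the estimated mean week 6 minus week 4 change on each diet (a fixed effect in the mixed model) with its 95% confidence interval, and by the diet-by-week interaction. The variance of subject-specific slopes will be reported as a supplementary measure of heterogeneity.

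The interval should carry the conclusion, not a non-significant p-value: a drift of 2.5 mg/dl would be significant for one diet in only about 28% of trials at SD 23.

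A pass/fail margin of half the Table 5 difference (5.1/2 = 2.55 mg/dl) should not be added. At SD 23 the per-diet interval of ±3.6 could not fit inside it. Pooled over diets, the half-width is 1.96 × 23/√480 = 2.06, so the estimate would have to lie within 2.55 − 2.06 = 0.49 of zero. With a standard error of 1.05, a truly steady trial would manage that only about 36% of the time.

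The cost is a short change of text. Both blood draws are already scheduled in every period, so no new data are needed.

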### 5. ORGANIZATIONAL STRUCTURE

The research team includes 2 field centers (one at Johns Hopkins University and another at Brigham and Women's Hospital, a data management and statistical unit at BWH, and a core laboratory at Washington University. The Steering Committee is the primary decision-making body. There are three standing subcommittees (Diet, Design/Measurements, and Recruitment/Study Coordinators). Ad hoc working groups are assembled as needed. A Data, Safety and Monitoring Committee is appointed to review and approve the protocol and then monitor all aspects of the trial.

The **Steering Committee** (co-chaired by the PIs of the field centers) includes the chair of each subcommittee; the lead dietitian from each center; and the data manager. During field work, the study coordinator from each center joins the Steering Committee. For the vast majority of deliberations, decision-making occurs by consensus. In the event that a consensus cannot be reached, the PIs of the field centers will vote formally. In the event that the PIs cannot reach agreement on a vital matter, the NHLBI project officer is asked to adjudicate. This committee is responsible for the overall design, conduct and analyses of the trial and for presentation and publication of trial results. To this end, it deliberates on all major issues, including protocol amendments.

The **Diet Subcommittee** (chair appointed by the Steering Committee) consists of the core dietitians from each site and the consultant dietitians. This subcommittee is responsible for all aspects related to menu development; food procurement, production, and distribution; hygienic issues; and adherence monitoring.

The **Design and Measurements Subcommittee** (chair appointed by the Steering Committee) consists of the co-investigators from each site and the data manager. This group is responsible for finalizing forms, developing data collection and training procedures, preparing the Manual of Operations, developing specimen collection and shipment procedures, and monitoring quality control at all levels (collection, entry and management of data; follow-up rates, etc).

A **Recruitment/Study Coordinators Subcommittee** (chair appointed by the Steering Committee) consists of recruitment and study coordinators from each center. This subcommittee reviews plans at each center, develops recruitment materials, and monitors progress on a regular basis.

A **Data**, **Safety and Monitoring Committee** (to include experts in biostatistics, hypertension, cardiovascular disease prevention, feeding studies, and clinical trialist) is appointed by the Steering Committee to review the protocol prior to field work and to monitor trial progress. Prevailing NIH and NHLBI policies will dictate the specific roles of this Committee.

Most of the committees convene by conference calls and at in-person Steering Committee meetings. The frequency of contacts varies during the trial. For instance, during the planning phase, the Steering Committee convenes at least monthly and the diet subcommittee more frequently.

#### 6. TIMELINE

*Planning*: Initially, the focus of the planning period is finalization of the protocol and menu development. The Manual of Operations, instruments and forms are then prepared, and data entry/management systems developed. Meal cycles are developed for each of 3 diets diet at each of 5 calorie levels. Menus are prepared, analyzed, and taste-tested. Recruitment planning also occurs.

Implementation: In contrast to DASH and DASH-Sodium, in which individuals were enrolled in nonoverlapping cohorts, participants in this trial are recruited in smaller waves that overlap. In this fashion, we avoid the wide swings in activities that complicated the conduct of the DASH and DASH-Sodium trials. Feeding for each wave lasts 19 weeks (1 week of run-in plus three 6 week periods) with at least 2 weeks separating each period. Recruitment for the initial cohort commences during the 3rd quarter of the first study year, in anticipation of initial feeding in the 4th quarter. Recruitment and feeding occurs in study years 2 - 4. As participants complete the trial, they receive participant-specific reports with their own data (averaged across study diets).

Analyses/closeout: Clinic closeout occurs in study year 5. During this period, clinical centers complete all data entry, respond to data edits and prepare summary reports of trial data for participants. During study years 4 and 5, laboratory specimens are analyzed; main results are prepared for publication and presentation.

### 7. SAFETY CONSIDERATIONS

This study does not involve any major risk to participants. Substantial effort has been made to identify and minimize potential risks. For instance, those persons who require pharmacologic therapy for elevated blood pressure or for dyslipidemia are excluded. Specifically, we exclude persons with systolic BP  $\geq$  160 mmHg and/or diastolic BP  $\geq$  100 mmHg. Such persons are informed of the elevated BP level and advised to consult with their physician. Likewise, diabetics, persons with prior or active cardiovascular disease, and persons with renal disease are excluded because the threshold for medication treatment of elevated BP is 130/85 mmHg in these persons (Class C hypertensives).

Each of the three study diets is reduced in saturated fat **and cholesterol**, and should therefore reduce LDL cholesterol. Furthermore, because each diet provides the micronutrient profile and fiber content of the DASH diet and because each diet provides just 100 mmol/day of sodium, each diet should reduce BP. The potential for BP reduction and for improved lipid profiles from the three diets greatly exceeds the negligible risks associated with participation in this trial.

Still, some persons may experience bloating and other minor gastrointestinal discomforts related to the high fruit, dairy and fiber content of the diets. It has been our experience that these problems resolve soon after changes in diet. For those persons with **presumptive** lactose intolerance, we will provide lactase tablets. Our experience suggests that GI discomfort is generally minor and subsides quickly. Participants are monitored for reactions to the diets and, if necessary, the diet can be modified or terminated. To minimize the risk of food-borne illness, kitchen staff follow all prevailing government hygienic regulations. Each of the metabolic kitchens is locally certified to prepare and distribute food.

Other potential risks of the study result from blood drawings. Venipuncture may cause some discomfort and/or bruising at the site of the puncture; and less commonly, the formation of a small blood clot or swelling of the vein and surrounding tissue and/or bleeding from the puncture site. Occasionally, blood drawing can cause someone to become dizzy, lightheaded or nauseated. All blood samples will be obtained by experienced personnel using small gauge needles.

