# Table 1: Inclusion and Exclusion Criteria of the Triat

# Inclusion Criteria

- Baseline SBP 120-159 mmHg or DBP 80-99 mmHg (mean over three screening visits) [note: stage 2 hypertension (SBP > 160 or DBP > 100 mmHg) based on the mean over three screening visits will be excluded, as well as a mean systolic BP > 170 or diastolic BP > 105 at any one visit]
- age 30 or older
- willing to eat at least one on-site meal/day, five days/week, and willing to eat study diets and nothing else for the 19 weeks of controlled feeding

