# **Medication Exclusions**

- Use of antihypertensive drugs (any in two months prior to SV1)
- Chronic use of medications that raise or lower blood pressure
- Use of a lipid lowering agent (any in 3 weeks prior to SV1)
- Unstable dose of hormone replacement therapy, psychotropic medications and thyroid hormone replacement therapy (defined as a change in dose within two months of the SV1 visit)
- Use of lithium, insulin, oral hypoglycemic agent, oral corticosteroid, anti-psychotic drugs, weight loss medications, oral breathing medication, nitrate, or digitalis

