# Medical History Exclusions

- Active or prior cardiovascular disease (stroke, MI, PTCA, CABG, congestive heart failure, symptomatic ischemic heart disease (angina), or ASCVD-related therapeutic procedure)
- Cancer diagnosis in past two years (however, persons with non-melanoma skin cancer, localized breast cancer, or localized prostate cancer can enroll if they did not require systemic chemotherapy)
- Inflammatory bowel disease, colostomy, malabsorption, or major GI resection
- Renal insufficiency as determined by a serum creatinine > 1.2 mg/dL for women or > 1.5 mg/dL for men. These participants can enroll if their estimated GFR is > 60 ml/min by either the Cockcroft-Gault equation or the simplified MDRD equation.
- Emergency room visit or hospital stay for asthma or COPD in last six months
- Any serious illness not otherwise specified that would interfere with participation

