# Laboratory Exclusions\*

- Fasting LDL cholesterol > 220mg/dL, triglycerides > 750 mg/dl, fasting blood sugar > 125 mg/dl
- Urine dipstick protein > 1+
- Serum transaminase > 2 times the upper range of normal, or a clinical diagnosis of hepatitis

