# **Other Exclusions**

- Consumption of more than 14 alcoholic drinks per week, or consumption of 6 or more drinks on an occasion, one or more occasions per week
- Significant food allergies, preferences, intolerances, or dietary requirements that would interfere with diet adherence
- Weight over 350 pounds
- Weight loss or gain of 10 pounds or more during prior 2 months
- Planning to leave the area prior to the anticipated end of participation
- Pregnant, breast feeding, or planning pregnancy prior to the end of participation
- Requirement for use of thigh cuff (arm circumference > 41 cm) or inability to obtain accurate blood pressure measurements
- Current participation in another clinical trial with an intervention that affects blood pressure or lipids
- Investigator discretion (e.g. for concerns over safety, adherence, or follow-up or for inappropriate behavior) reasons
- Vitamin, fish-oil, weight-loss, soy, mineral, or herbal supplements that cannot be stopped prior to run-in

\* For any laboratory-based exclusion, one repeat laboratory test is permitted if the initial value would have excluded the individual

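### Section 7 says diabetics are excluded, but Table 1 lists no diagnosis of diabetes as an exclusion, so some drug-untreated diabetics can enter

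*Protocol*

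**What the plan says.** Section 7 (Safety Considerations) opens its safety case by saying that persons who need drug treatment for blood pressure or lipids are kept out. It supports this with the exclusion of stage 2 blood pressure, and then with a second group, in the words "diabetics, persons with prior or active cardiovascular disease, and persons with renal disease are excluded because the threshold for medication treatment of elevated BP"; the figure it goes on to give, for all three groups, is 130/85 mmHg. The sentence is unqualified.

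Table 1 (section 4.1) sets the criteria themselves. Its inclusion line is "Baseline SBP 120-159 mmHg or DBP 80-99 mmHg (mean over three screening visits"). Two of its exclusions bear on diabetes:

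- Medication Exclusions: "Use of lithium, insulin, oral hypoglycemic agent, oral corticosteroid" and other listed drugs.
- Laboratory Exclusions: "fasting blood sugar > 125 mg/dl". The table's footnote adds that "one repeat laboratory test is permitted if the initial value would have excluded the individual".

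The Medical History Exclusions name cardiovascular disease, cancer, gastrointestinal disease, renal insufficiency, and recent acute care for asthma or COPD. They close with a catch-all for other serious illness that would get in the way of taking part. Diabetes is not among them.

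**The concern.** Section 7 gives one reason for excluding three groups: by its own account, they would be candidates for blood pressure drugs from 130/85 mmHg. Cardiovascular disease has a matching history exclusion in Table 1, and renal insufficiency has a matching criterion. Diabetes, the first group named, is caught only indirectly, through drug use and a fasting glucose value. A diagnosed diabetic who is on no drug and whose glucose is below the cut-off passes both.

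At stake is whether a stated participant protection is true. Section 5 has the Data, Safety and Monitoring Committee review the protocol before field work, and on this point that review would rest on an assurance that the criteria do not carry out. There is also a practical side. Under section 9, a computer program confirms that all eligibility criteria are met before randomization. A criterion that appears only in the safety narrative may or may not be checked there, and the two sites could apply different rules.

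**Working it through.** The check is a comparison of texts. It depends on no power or alpha figure.

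**1. The three groups in section 7 against Table 1**

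| Group in section 7 | Criterion in Table 1 |
|---|---|
| Cardiovascular disease | Named history exclusion |
| Renal disease | Named criterion: creatinine cut-offs with an estimated-GFR exception, plus a dipstick protein limit |
| Diabetes | No diagnosis or history; only drug use and fasting glucose > 125 mg/dl |

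**2. Who passes the diabetes-related criteria.** I read the footnote as admitting a person whose repeat value is within the limit. The glucose values are illustrative.

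| Diagnosed diabetic, treatment | First glucose (mg/dl) | Repeat | Outcome under the named criteria |
|---|---|---|---|
| Insulin or oral agent | any | any | Excluded |
| No glucose-lowering drug | 110 | not needed | Admitted |
| No glucose-lowering drug | 125 | not needed | Admitted |
| No glucose-lowering drug | 130 | 120 | Admitted |
| No glucose-lowering drug | 130 | 130 | Excluded |

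The gap is therefore confined to diagnosed diabetics on no glucose-lowering drug with fasting glucose of 125 mg/dl or less on one of at most two tests.

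**3. Blood pressure of those admitted.** The systolic entry range of 120 to 159 mmHg covers 40 whole-number values, of which 130 to 159, that is 30, are at or above section 7's systolic figure. The diastolic range of 80 to 99 mmHg covers 20 values, of which 85 to 99, that is 15, are at or above its diastolic figure. These counts describe the width of the range, not the share of participants. A person at 142/88 mmHg, for example, is inside the entry range and above 130/85 mmHg on both components.

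**4. Time in the trial.** Feeding lasts 1 + 3 × 6 = 19 weeks (section 6). With two washouts of at least 2 weeks each, the minimum from the start of run-in is 19 + 2 × 2 = 23 weeks.

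**5. Number affected.** The protocol gives no figure. If 1% to 3% of the 160 participants were such persons, the count would be 0.01 × 160 = 1.6 to 0.03 × 160 = 4.8, or about 2 to 5. The percentages are an assumption with no source in the protocol.

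**The case against.** The best defence is that section 7 is a narrative summary and that Table 1 carries out the diabetes exclusion in operational form, through drugs and glucose. Together these two criteria remove every drug-treated diabetic and everyone who stays above 125 mg/dl. Other screens exist as well: the serious-illness catch-all, investigator discretion that expressly mentions safety, a medical eligibility questionnaire, and review of the eligibility laboratory results by a clinician-investigator. Blood pressure readings are shared with participants before randomization, and blood pressure is measured at least weekly during feeding.

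Much of this stands, and it makes the gap narrow. It does not close it. The catch-all applies only to illness that would interfere with taking part, discretion is optional, and neither names diabetes. Monitoring is not the promised exclusion: the escape levels in section 8 begin above 170 systolic or 105 diastolic, far from 130/85 mmHg, and section 9 keeps diet-specific readings from participants until the end of the trial.

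A reader might infer two further faults that the protocol does not support.

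- **Renal disease.** Table 1 says of persons with raised creatinine that "These participants can enroll if their estimated GFR is > 60 ml/min" by either of two equations, and it tolerates 1+ dipstick protein. One might call this a second contradiction of section 7. But Table 1 gives a working definition of renal insufficiency, and nothing in the protocol says that raised creatinine with a GFR above 60, or 1+ protein, amounts to renal disease. A summary term next to its operational definition is not a contradiction.
- **The glucose and insulin aim.** One might say that Specific Aim 3 loses its intended population. But section 2 sets the aims in all enrolled participants, no text promises a diabetes-free population for Aim 3, and the section 4.11 contrasts are within person. Section 7 gives only the blood pressure threshold as its reason. No bias or loss of precision for Aim 3 has been shown.

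**Conclusion.** The point holds for diabetes only. Section 7 states an unqualified exclusion that Table 1 does not fully carry out, and the entry blood pressure range extends well above the threshold given as the reason for it. It would be too strong to say that Table 1 admits diet-controlled diabetics in general, because those whose fasting glucose exceeds 125 mg/dl on both tests are excluded.

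The size is small and not known from the documents; the 2 to 5 participants rest wholly on the assumed 1% to 3%. The conclusion itself rests on two readings: that the footnote admits a person whose repeat glucose is within the limit, and that the general clauses cannot be counted on to exclude a condition they do not name. This is an inconsistency in eligibility text, and eligibility belongs in the protocol and not in an analysis plan. It is worth correcting because a stated protection should either be true or be withdrawn.

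**What to change.** Reconcile section 7 with Table 1 so that both describe the same population. There are two routes, and the documents do not show which is intended:

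- If section 7 states the intent, make Table 1 carry out the exclusion of diabetics that section 7 describes. The health questionnaire that Table 3 already schedules at the first screening visit and at run-in could carry any question needed.
- If Table 1 states the intent, reword the sentence in section 7, and the safety argument that rests on it, to describe the persons whom Table 1 actually excludes.

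This review takes no view on which rule is clinically right. Whichever route is taken, the eligibility check before randomization in section 9 should follow the reconciled text.

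The first route costs one eligibility line and at most a few more screen failures. The second costs a reworded sentence and a weaker safety statement. Neither affects the sample size, the outcomes or the analysis.
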